- The distribution of stereoacuity scores will be tabulated by treatment group at baseline and at each followup visit. Medians and ranges of stereoacuity scores for all visits will be computed by treatment group. Change in ranked stereoacuity scores (≥ 2 levels worse, within 1 level, ≥ 2 levels better) from baseline to
- the 4- and 8-week visits will be tabulated for each group and compared between treatment groups using
- the exact Wilcoxon rank sum test.
- 258

261

4.3 Treatment Compliance, Dose & Game Performance with Binocular Therapy (Binocular Treatment Group)

- In addition to subjective compliance with prescribed treatment based on parent-reported calendars, an
- objective measure of compliance will be obtained from the automated iPad log files for those assigned to
- binocular treatment. The iPad log files record total time playing the game and the contrast level presented
- to the fellow eye. The following sections describe exploratory analyses for compliance measures,
- treatment dose, and game performance in the binocular group. The analyses will be limited to
- 269 participants who completed the follow-up visits within the pre-specified analysis windows (section 3.3).
- 270 No adjustment for multiplicity will be made to these exploratory analyses.
- 271

272 4.3.1 Binocular Treatment Dose, Compliance and Fellow-eye Contrast

- 273 Participants will be prescribed 1 hour per day of binocular game play for 5 days per week as per protocol.
- The cumulative amount of binocular treatment received since baseline (dose) and the percentage of
- prescribed treatment completed (compliance) will be calculated from the log file data for the 4- and 8-
- week visits. Compliance will be calculated as the total amount of binocular treatment received divided by
- the total number of prescribed hours at that time point since baseline. For each follow-up visit, the
- distribution of the cumulative hours of treatment received since baseline (0 to <10, 10 to <20, etc.) and
- the percentage of prescribed treatment completed (0% to 25%, >25% to 50%, >50 to 75%, >75%) will be
- tabulated with computation of descriptive statistics (median and range).
- 281
- 282 The change in contrast level presented to the fellow eye provides a measure of game performance because
- the contrast level in the fellow eye is incremented based on ≥ 15 minutes (or ≥ 30 minutes for participants

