- 317 Only 22% of subjects randomized to the binocular game performed >75% of the prescribed
- 318 treatment (median 46%, interquartile range 20% to 72%). In younger subjects 5 to <7 years of
- 319 age, without prior amblyopia treatment, amblyopic-eye VA improved 2.5 ± 1.5 lines in the
- 320 binocular group and 2.8 ± 0.8 in the patching group. Adverse effects (diplopia, reduction of
- 321 fellow-eye VA, new tropia) were uncommon and of similar frequency between groups.
- 322
- 323 We therefore concluded that in children 5 to <13 years of age, amblyopic-eye VA improved
- 324 with both binocular game play and patching, particularly in younger children age 5 to <7 years
- 325 without prior amblyopia treatment. However, based on a post hoc analysis, VA improvement
- 326 with this particular binocular iPad treatment was not as good as with 2 hours of prescribed daily
- 327 patching.

328 1.3 **Rationale for Proposed Study Design**

329 It is entirely possible that our failure to find non-inferiority of binocular treatment to part-time

- 330 patching in our recent RCT was due to poor compliance with the binocular treatment. Only 22%
- 331 of subjects randomized to the binocular game performed >75% of the prescribed treatment
- 332 (median 46%, interquartile range 20% to 72%).
- 333

- 334 Recently, a new binocular game has been developed for children, called "Dig Rush," which is
- much more interesting than the falling blocks game because it involves more interesting tasks
- such as digging for gold and earning rewards. It has 42 levels, and therefore the child remains
- and engaged for a much longer period of time than the falling blocks game.
- 338
- 339 The Birch group has studied the binocular Dig Rush game in children age 4 to <10 years and
- found that compliance with the game is excellent, with a mean amblyopic eye VA improvement of 1.5 lines at 2 weeks and 1.7 lines at 4 weeks.²⁶
- 342

355

362

363

364

365

367

381

- 343 Based on several promising pilot studies of binocular treatment in children and in adults, a full
- RCT is warranted, to investigate whether binocular treatment is an effective treatment for
- amblyopia, and, analogous to the PEDIG RCT which investigated the effectiveness of
- 346 patching,²⁷ the appropriate control group is continued spectacle treatment alone.

347 **1.4 Study Objective**

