600 Subjects assigned to the binocular treatment group will be prescribed the Dig Rush game to play for 601 1 hour per day, 5 days a week for 8 weeks. Parents of subjects will be instructed that the 1 hour of 602 daily treatment should be completed in a single 60-minute session, but if this is not possible for 603 whatever reason, the treatment may be divided into shorter sessions totaling 1 hour per day.

604

All subjects in the study will play the Dig Rush game presented on an iPad while wearing red/green (anaglyph) glasses (over current spectacle correction, if applicable) with the green filter placed over the amblyopic eye. The subject should be instructed to hold the iPad at his/her usual reading distance. Some game elements are only visible to the fellow eye viewing through the red lens, while other game elements are only visible to the amblyopic eye viewing through the green lens. Image contrast varies depending on depth of amblyopia to ensure stimulation of the amblyopic eye and binocular game play.

612

613 Contrast of the game elements in the amblyopic eye will be at 100% throughout the study. Contrast

of game elements seen by the fellow eye will begin at 20% at the start of the study and will increase

or decrease automatically in increments from the last contrast level (e.g., 20% to 22%) based on the

616 subject's performance and duration of game play.

617 **3.2** Continued Spectacle Correction Group

618 Subjects assigned to the continued spectacle wear group will continue wearing their appropriate

619 spectacle correction (if required) for all waking hours, 7 days per week for 8 weeks. Subjects

620 assigned to the continued spectacle wear group will be offered binocular treatment for 8 weeks after

621 the initial 8 weeks of the study has been completed. Subjects in the continued spectacle correction

- 622 group that choose to continue with binocular treatment after 8 weeks will return for a follow-up
- 623 visit at 16 weeks.

624 **3.3** Compliance

Parents will be asked to complete a compliance calendar by manually recording the number of minutes that the child played the game each day, and/or how long the child has worn the spectacle correction. The investigator will review the calendars at each follow-up visit. The amount of time the game is played will also be recorded automatically during game play by the iPad. These data will be downloaded at the Jaeb Center when the iPad is returned after the study.

630 **3.4** Phone Call

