5.4.2.3 Treatment Compliance with Binocular Therapy

1012 Data from the automated iPad log files will be used to provide an objective measure of compliance 1013 with binocular treatment. The total amount of game play will be computed for the initial 4 weeks of 1014 treatment for the binocular treatment group. Secondary analyses will evaluate the relationship

1015 between the total amount of game play with (1) change in VA and (2) change in stereoacuity after

- 1016 the first 4 weeks of binocular treatment.
- 1017

1018 **5.4.2.4** Fellow-eye Contrast with Binocular Therapy

1019 Data from the automated iPad log files will be used to assess game performance as measured by the 1020 fellow-eye contrast. The level and change in fellow-eye contrast will be computed for the initial 4 1021 weeks of treatment for the binocular treatment group. Secondary analyses will evaluate the 1022 relationship between the change in fellow-eye contrast with (1) change in VA and (2) change in 1023 stereoacuity after the first 4 weeks of binocular treatment.

1024 5.4.3 Safety 1025

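### SAP 4.3 limits the iPad-log summaries of dose, compliance and contrast to binocular-group children with in-window visits; a summary over all randomised children with a log should be added

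*SAP*

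**What the plan says.** SAP 4.3 introduces the compliance, dose and game-performance sections with one analysis set for all of them: "participants who completed the follow-up visits within the pre-specified analysis windows (section 3.3"). It labels the material exploratory ("The following sections describe exploratory analyses for compliance measures"). SAP 4.3.1 defines the measure: "Compliance will be calculated as the total amount of binocular treatment received divided by" the hours prescribed up to that time point. It ties dose to the 4- and 8-week visits and contrast to the visit date.

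Protocol 5.4.2.3 plans the same summary differently: "The total amount of game play will be computed for the initial 4 weeks of" treatment in the binocular group, with no visit or window condition.

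Protocol 3.3 describes the data source. Playing time will "also be recorded automatically during game play by the iPad", and the data are "downloaded at the Jaeb Center when the iPad is returned after the study".

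The windows in SAP 3.3 are 21 to <49 days and 49 to <105 days. That section applies them by name to amblyopic-eye VA and stereoacuity only.

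**The concern.** A missed or late examination does not stop the iPad recording, so the 4.3.1 summaries need no visit. Limiting them to in-window attenders selects on attendance, which is plausibly linked to compliance. A family that has stopped playing is likelier to miss the visit, and its child then leaves both numerator and denominator.

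Objective compliance will be read closely. Protocol 1.3 offers poor compliance as a possible reason for the result of the earlier binocular trial (ATS18). Protocol 5.2 expects a larger effect here because of better compliance. Protocol 5.1 powers the age cohorts separately because compliance may differ by age. A figure conditioned on attendance does not say how well the game was taken up by all children assigned to it.

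**Working it through.** **Inputs from the documents.** Younger cohort 182 (91 per group) and older cohort 116 (58 per group); 5% loss to follow-up (Protocol 5.3); windows as in SAP 3.3; prescribed play of 5 hours per week, so 20 hours at 4 weeks and 40 at 8 weeks. For ATS18, Protocol 1.2 gives 22% with >75% compliance, median 46%, interquartile range 20% to 72%.

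**Assumed.** Exclusion above 5%, and reported compliance shares of about 40% and 60%. The documents state no expected compliance for this trial.

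**The plan's own figures.** A two-sided t-test at 5% with 90% power, difference 0.75 lines and SD 1.5 gives 172 in total. Then 86/0.95 = 90.5, so 91 per group and 182 in total, as stated. For the older cohort, SD 6 letters and difference 3.75 give 110; 55/0.95 = 57.9, so 58 per group and 116. Group sizes and the 5% allowance are therefore consistent.

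**Bound on the share with >75% compliance.** Let p be the in-window share and d the excluded fraction. The all-randomised share lies between p(1 − d), if no excluded child passed 75%, and p(1 − d) + d, if all did. The largest overstatement is p × d.

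| Group size | Excluded | In-window share | All-randomised, lowest | All-randomised, highest | Largest overstatement (points) |
|---|---|---|---|---|---|
| 91 | 5 | 19/86 = 22.1% | 19/91 = 20.9% | 24/91 = 26.4% | 1.2 |
| 91 | 5 | 34/86 = 39.5% | 34/91 = 37.4% | 39/91 = 42.9% | 2.2 |
| 91 | 5 | 52/86 = 60.5% | 52/91 = 57.1% | 57/91 = 62.6% | 3.3 |
| 58 | 3 | 12/55 = 21.8% | 12/58 = 20.7% | 15/58 = 25.9% | 1.1 |
| 58 | 3 | 33/55 = 60.0% | 33/58 = 56.9% | 36/58 = 62.1% | 3.1 |

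With 91 per group and shares of about 22% to 60%, the largest overstatement is 2.2 to 5.9 points at an assumed 10% exclusion, 3.4 to 9.2 at 15%, and 4.3 to 11.9 at 20%.

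**Bound on the median.** If all excluded children rank lowest, the all-randomised median is the (0.5 − d)/(1 − d) quantile of the in-window set. At d = 0.05 this is the 47.4th percentile. Interpolating linearly between the ATS18 lower quartile and median, as an assumed shape, gives 20 + (0.474 − 0.25)/0.25 × 26 = 43.3%, against 46% in window. At 10%, 15% and 20% exclusion it is 40.2%, 36.8% and 33.0%.

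**Scale.** The standard error of a comparison of 22% in 86 with 22% in 190 (the ATS18 binocular group) is √(0.22 × 0.78/86 + 0.22 × 0.78/190) = 5.4 points, larger than the bound at 5% loss.

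**Visit timing.** A child who plays exactly as prescribed has 21 × 5/7 = 15.0 hours at day 21 and 48 × 5/7 = 34.3 at day 48. Both days fall in the 4-week window, but the hours fall in different bands of the 10-hour tabulation in SAP 4.3.1. Visit-based hours therefore mix adherence with timing. A fixed day 28 restores the protocol's initial 4 weeks.

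**The case against.** The strongest objection is that the in-window set is the right one for interpreting the VA result. SAP 4.1 limits the primary analysis to the same kind of in-window attenders, so children outside the window cannot affect that estimate. This stands. A reader might infer that the restriction would wrongly weaken poor compliance as an explanation of a null primary result. The documents do not support that inference, because in-window compliance describes the children who produced the estimate. The all-randomised figure answers a different question, namely uptake among everyone assigned the game. It belongs beside the in-window figure and should not replace it.

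A reader might also infer that the restriction makes the result non-comparable with ATS18. Protocol 1.2 words that figure per randomised child ("Only 22% of subjects randomized to the binocular game performed >75% of the prescribed" treatment) but does not give its analysis set. Both 42/190 and 40/180 round to 22%, so the denominator cannot be recovered. The comparison is limited in any case: ATS18 ran 16 weeks at 7 days a week with ages pooled.

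Four further points stand in part:

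- Recording is independent of visits, but retrieval is not independent of follow-up: "These data will be downloaded at the Jaeb Center when the iPad is returned after the study". Some lost children may have no log under any analysis set.
- The direction of bias is plausible, not shown. The windows are wide, Protocol 4.2 expects very few withdrawals, and late attenders may comply well. Under Protocol 3.6, children whose amblyopia has resolved may stop play but still attend, which lowers reported compliance.
- SAP 4.5 reports visit completion and calendar-based compliance by group with no stated window limit, so the restriction affects the log summaries only.
- The analyses are exploratory.

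None of this gives a reason for requiring a visit in a descriptive summary of log data.

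**Conclusion.** The concern holds in a limited form. SAP 4.3 imposes a visit condition on the 4.3.1 summaries that Protocol 5.4.2.3 does not contain and the data do not need. Reported compliance is likely to be somewhat too high as a description of all children randomised to the game. At the planned 5% loss, the excess is at most about 1 to 3 points in the share with >75% compliance, for reported shares of about 22% to 60%. That maximum assumes that no excluded child passed 75%. Larger values need an excluded fraction above 5%, for which the documents give no basis. The primary VA result is unaffected, and comparability with ATS18 cannot be judged from the documents. The point is minor but easily corrected.

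**What to change.** In SAP 4.3.1, add a summary of dose, percentage of prescribed play and fellow-eye contrast at day 28 and day 56 from randomisation. Include every child randomised to the binocular group whose log can be retrieved, whether or not the visit was attended or in window. Report the number without a log, and add a bound for dose and compliance that counts those children as zero hours.

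Keep the in-window summary beside it, labelled as matching the VA analysis set. Keep the window restriction in 4.3.3 and 4.3.4, which relate log data to an examination result.

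The cost is a change of SAP wording and a small amount of extra tabulation from logs already due for download when iPads are returned. The compliance figure may come out slightly less favourable.

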4.3.3 Visual Acuity Change according to Binocular Treatment Dose & Change in Fellow-eye

298 Contrast

The relationship between change in amblyopic-eye VA from baseline to the 4- and 8-week visits with respect to 1) cumulative binocular treatment dose and 2) change in fellow-eye contrast will be examined using scatterplots for evidence of association and form of association. Pairwise correlation between VA change and each of the two factors will be computed using Pearson correlation coefficients if there is evidence of a linear trend based on the scatterplots.

304

305 If there is evidence of a linear relationship between amblyopic-eye VA change from baseline to 4 weeks

306 with either cumulative treatment dose or change in fellow-eye contrast at 4 weeks, a multivariable

regression model that adjusts for baseline VA will be fit to describe this relationship. Collinearity

308 diagnostics will be output from the multivariable regression model to assess whether it is appropriate to

retain both factors in the model. If the two factors are highly collinear, separate regression models will be

310 fit to evaluate the relationship between change in amblyopic-eye VA with each individual factor, adjusted

311 for baseline VA. The analyses described above will also be repeated for the 8-week visit if appropriate.
312

313 Model assumptions for the multivariate regression models will be assessed as described in section 4.1. If

the assumption of linearity between change in amblyopic-eye VA and any of the aforementioned factors

- is not met, then this factor will be categorized into quartiles based on the distribution of the data.
- 316

Given that all participants will be prescribed the same dose of binocular therapy, any differences in

cumulative treatment dose between participants would only be due to treatment compliance, which could

319 be affected by the efficacy of the binocular treatment, differences in motivation to comply with prescribed

treatment and potentially other unmeasured factors. Therefore, results of these analyses will be

- 321 interpreted with caution.
- 322

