4.3.4 Stereoacuity Change according to Binocular Treatment Dose & Change in Fellow-eye Contrast

The relationship between change in stereoacuity from baseline to the 4- and 8-week visits with respect to

1) cumulative binocular treatment dose and 2) change in fellow-eye contrast from baseline will be

examined using scatterplots and Pearson correlation coefficients as described in section 4.3.3. For this

analysis, a logarithm (base 10) transformation will be applied to the raw stereoacuity scores and the

difference between the log converted baseline and follow-up scores will be computed as described insection 3.2.

331

332 If there is evidence of a linear relationship between change in stereoacuity from baseline to 4 weeks with

either cumulative treatment dose or change in fellow-eye contrast at 4 weeks, a multivariable regression

model that adjusts for baseline stereoacuity will be fit to describe this relationship. The same modeling

approach as described in section 4.3.3 will be used. If appropriate the analyses will also be applied to the

8-week visit. As noted in section 4.3.3, results of these analyses will be interpreted with caution.

337

338 4.4 Safety Analyses

- 339 Statistical significance for each formal group comparison of safety outcomes/adverse events was tested at
- a type I error rate of 1% to adjust for multiple testing. Given that spectacle wear and game play on an
- iPad device are not invasive treatments and pose minimal risk, if any, to participants, there are greater
- 342 concerns about the possibility of falsely finding a group difference in safety outcomes/adverse events than
- in missing a difference. Safety analyses will include all participants who completed the follow-up visits
- 344 regardless of the analysis windows.
- 345

346 4.4.1 Visual Acuity in the Fellow Eye

The distribution of change in fellow-eye VA from baseline to 4 weeks will be tabulated. The mean

- change in fellow-eye VA from baseline to 4 weeks will be calculated and compared between treatment
- 349 groups using ANCOVA with adjustment for the baseline fellow-eye VA. The proportion of participants 350 with loss of $\geq 2 \log$ MAR lines (≥ 10 letters) of VA in the fellow-eye from baseline to the 4-week exam
- with 1055 of $\frac{1}{2}$ 2 logMAR lines ($\frac{1}{2}$ 10 letters) of VA in the renow-cyc noni baseline to the 4-week exam 351 will be reported by treatment group and compared using Barnard's exact test. The analyses will be

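### A collinearity check, not the question asked, decides whether SAP 4.3.3 reports the dose slope for total play time or a slope conditional on fellow-eye contrast

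*SAP*

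**What the plan says.** The protocol lists two separate secondary analyses in the binocular group. Section 5.4.2.3 asks for the relationship "between the total amount of game play with (1) change in VA and (2) change in stereoacuity after" the first 4 weeks. Section 5.4.2.4 asks for the "relationship between the change in fellow-eye contrast with (1) change in VA and (2) change in" stereoacuity. Neither mentions holding the other factor fixed. Section 5.4.4 repeats the analyses at 8 weeks.

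SAP 4.3.3 proceeds in stages:

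- It starts with scatterplots. "Pairwise correlation between VA change and each of the two factors will be computed using Pearson correlation coefficients" if these look linear.
- If acuity change shows a linear relationship "with either cumulative treatment dose or change in fellow-eye contrast at 4 weeks, a multivariable" regression adjusted for baseline acuity follows.
- Collinearity diagnostics then decide whether to "retain both factors in the model. If the two factors are highly collinear, separate regression models will be" fitted, one per factor, each adjusted for baseline acuity. No diagnostic threshold is given.

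SAP 4.3.4 carries this over to stereoacuity: the same "approach as described in section 4.3.3 will be used. If appropriate the analyses will also be applied to the" 8-week visit.

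SAP 4.3.1 describes how contrast moves: "the contrast level in the fellow eye is incremented based on ≥ 15 minutes (or ≥ 30 minutes for participants" enrolled from 24 August 2018), with the added condition that the previous day's play was successful. Protocol 3.1 says contrast can go down as well as up, depending on performance and duration of play.

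**The concern.** By the SAP's own account, change in contrast is measured after baseline and is produced partly by play time and partly by success at the game. A model holding both factors therefore answers a different question from a dose-only model. It asks whether more play goes with more acuity gain among children with the same contrast gain. Any benefit of play that acts through rising contrast is left out of that slope.

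Collinearity diagnostics describe precision. They carry no information on whether the total or the conditional relationship is wanted, yet here they choose between them. Without a cut-off, one cohort or visit could report a total slope and another a conditional slope, both labelled as dose. The 15- and 30-minute rules, split by enrolment date, could also change the built-in correlation between cohorts.

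At stake is the reading of dose. Protocol 1.3 raises poor compliance as a possible reason for the earlier trial's result, so readers will look at whether more play went with more improvement.

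**Working it through.** The documents give no slope, power or collinearity threshold for this analysis, so there is no plan figure to reproduce.

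**1. Planned question against reported slope**

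| Source | Dose quantity |
|---|---|
| Protocol 5.4.2.3 | Play time with outcome change, contrast not held fixed |
| SAP 4.3.3, split models | Dose slope adjusted for baseline: the same quantity |
| SAP 4.3.3, joint model | Dose slope adjusted for baseline and contrast gain: a different quantity |

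**2. Algebra**

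For a given baseline acuity, write contrast gain = a·dose + u, and acuity change = d·dose + c·contrast + e.

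- Dose-only slope: d + a·c, the total relationship (u and e unrelated to dose).
- Joint slope, with u and e unrelated: d. The part a·c is lost.
- Joint slope, if a performance trait links u and e, with k = cov(u, e)/var(u): d − a·k. With a and k positive this is too low and can be negative.
- If c = 0 and k = 0, both slopes equal d, and the joint model only costs precision: the SE grows by about √VIF, where VIF = 1/(1 − r²) and r is the dose-contrast correlation.

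**3. Inputs for illustration**

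- Binocular arm after 5% loss: 91 × 0.95 ≈ 86 (younger) and 58 × 0.95 ≈ 55 (older), from the totals of 182 and 116 in Protocol 2.1.
- Adherence: median 46%, quartiles 20% and 72% (Protocol 1.2). This is an earlier trial of another game over 16 weeks.
- Prescribed play by 4 weeks: 4 × 5 = 20 days, so 20 hours.
- Contrast step: 2 points or 10% of the last level, both consistent with the 20%-to-22% example in Protocol 3.1. Trigger: 15 or 30 minutes (SAP 4.3.1).
- Assumed, not from the documents: shape of the adherence distribution, success probability, whether and when contrast falls, residual SD of 1.2 lines, and all true effects.

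**4. How collinear would the factors be?**

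| Assumed contrast rule | r | VIF | SE multiplier √VIF |
|---|---|---|---|
| Success probability 0.8, one step down on other days | 0.53–0.75 | 1.4–2.3 | 1.18–1.51 |
| Contrast can fall, day-to-day variation in play, n = 86 | 0.59–0.84 | 1.6–3.6 | 1.26–1.90 |
| Steps up only, 16 settings | 0.74–0.94 | 2.3–9.6 | 1.5–3.1 |

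End-point check for the first row: 1/(1 − 0.53²) = 1.39, root 1.18; 1/(1 − 0.75²) = 2.29, root 1.51. VIFs in the other rows are means over simulated trials.

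With a VIF > 5 rule, the second row splits the factors in at most 3% of trials, and the third row in 0% to 100% depending on the setting. With VIF > 10 the third row splits in 0% to 38%. The branch therefore depends on an unstated cut-off and on game behaviour the documents do not fully specify.

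**5. What happens to the dose slope when both factors stay in?**

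Steps-up-only settings, 400 simulated trials per cell, least squares adjusted for baseline, lines per hour:

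| Assumed truth | Dose-only slope | Joint dose slope |
|---|---|---|
| All effect through contrast | 0.018 to 0.050 | −0.002 to 0.011 |
| All effect direct | 0.048 to 0.051 | 0.045 to 0.054, SE 1.5 to 3.1 times larger |
| Mixed | 0.033 to 0.048 | 0.017 to 0.033 |
| Direct, plus a performance trait driving contrast and acuity | 0.047 to 0.053 | −0.052 to −0.013 |

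For scale, 0.05 lines per hour × 20 hours = 1 line at full dose. The dose-only model recovered the total slope in every scenario, with SE from about 0.023 (n = 86) to 0.031 (n = 55).

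**The case against.** A reader might infer that the reported dose slope is never the one the protocol asks for, or that either branch gives a wrong answer. The documents do not support that. In the split branch the SAP fits exactly the two baseline-adjusted relationships that Protocol 5.4.2.3 and 5.4.2.4 list. Nor does the protocol require the contrast relationship to be net of play time, so a contrast-only slope is not a departure from it. This part of the objection stands in full.

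A dose scatterplot, and a Pearson correlation if it looks linear, are planned in either branch, so readers would see the unconditional association. That softens the consequence. It does not remove the point, because the correlation is not adjusted for baseline and gives no slope.

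The SAP calls these analyses exploratory and warns that dose differences reflect compliance, motivation and unmeasured factors. That is true, and it means no model here identifies a causal dose-response. But the warning concerns why dose varies. It does not tell the reader that the dose coefficient changes meaning between branches.

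SAP 4.3.2 already examines the dose-contrast relationship, and 4.3.1 states the increment rule. Neither says that the correlation is partly built in by the game.

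Finally, the adherence figures come from another game, and Protocol 1.3 describes compliance with Dig Rush as excellent. The illustration cannot be read as a forecast.

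**Conclusion.** The point holds for the joint branch. When both factors are retained, SAP 4.3.3 and 4.3.4 report only a conditional regression slope for dose, which is not the relationship in Protocol 5.4.2.3. A collinearity result with no threshold decides whether this happens. The conclusion rests on the SAP's description of how contrast is incremented, not on the simulations.

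The size is unknown. On assumed inputs the joint dose slope could be unbiased but less precise, attenuated, near zero or reversed. Which of these applies depends on how far any benefit acts through contrast and on whether performance drives both contrast and acuity. The documents give neither. It would be tempting to say that the dose slope is halved, or that the trial would conclude that more play does not help. Either would need a mediated share that no document supplies.

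The scope is limited: exploratory analyses (secondary in the protocol), binocular arm only, already marked for cautious reading. The primary comparison is unaffected. This is a worthwhile wording correction, not a threat to the trial's main result.

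**What to change.** Stop using collinearity to choose the model in SAP 4.3.3, and by reference in 4.3.4. Once the regression step is triggered, always report the following at 4 and 8 weeks, for acuity and for stereoacuity:

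- a dose-only model adjusted for the baseline value, as the analysis for Protocol 5.4.2.3;
- a contrast-only model adjusted for the baseline value, as the analysis for Protocol 5.4.2.4.

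A joint model may be added as supplementary, with each coefficient labelled as conditional on the other factor and the collinearity diagnostics shown beside it for information. Replacing the contrast-only model with a dose-adjusted one would not do, because the relationship in Protocol 5.4.2.4 would then have no regression of its own.

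Add one sentence to SAP 4.3.2 saying that a correlation between dose and contrast is partly built in by the game's increment rule.

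The cost is SAP wording and a few extra exploratory models on the same data. The revision history places version 4.0 at the drafting of the younger-cohort manuscript, so the change should be dated and marked there as made at that stage or later.
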